2.4 ENDPOINTS

Primary Endpoints

Feasibility: An indication of feasibility assessed by calculating treatment adherence indicators such as the average number of therapy sessions completed by participants, the percentage of participants completing different components of the intervention (face-to-face sessions, phone calls), and attrition (the percentage who complete post-intervention assessment).

Acceptability: An indication of acceptability assessed by calculating scores on Credibility/Expectancy Scales, the Client Satisfaction Questionnaire, User Experience Questionnaire and other bespoke acceptability measures identified by the YPAG, and by analysing qualitative data obtained through the Experience of Service questionnaire and semi-structured feedback interviews.

Safety: Safety of the intervention determined by reviewing *adverse events* recorded at each assessment and therapy session/phone call contact.

Secondary Endpoints

Potential effectiveness of the IMAGINATOR intervention:

Change assessed from pre-FIT intervention to post-FIT intervention, and at 6 months follow up in the following outcomes:

- a) Average frequency of self-harm, and average severity of self-harm scores over the past 3 months
- b) Average scores on questionnaires of clinical, functional and process outcomes (see Assessments)
- c) Proportion of YP needing further treatment in CCAMHS/MINT/other WLT services vs can be closed to CCAMHS/MINT/other WLT services
- d) Emergency department visits.

Potential mechanisms:

Change assessed from pre-FIT intervention to post-FIT intervention, and at 6 months follow up in the following outcomes:

- a) Average scores on characteristics of mental imagery associated with self-harm when present (e.g. vividness, compellingness)
- b) Average scores of the urge to self-harm
- c) Average scores on emotion regulation ability measures.

Potential effectiveness of the *IMAGINATOR* app:

a) Correlations between endpoint scores (listed above) and the following measures of *IMAGINATOR* app use: number of app sessions/logins and total duration of app use, number of activity cycles completed, number of personalised media uploaded, number of completed guided imagery sessions, total duration of guided imagery completed and use of any other key functionalities at 6 months follow up.

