Collection of Baseline Measures: Eligible participants are then asked to complete further baseline questionnaires and interviews (see 3.7 Assessments and Questionnaires) assessing: the presence, characteristics and frequency of self-harming behaviour; demographic characteristics; measures of clinical and functional outcomes; and measures of characteristics and processes associated with self-harm and with FIT (e.g. mental imagery characteristics). All questionnaires are standard tools, which are commonly used in psychological studies. Specially designed measures for this study are: the *Timeline Follow Back Technique to assess self-harm frequency;* the *Two items questionnaire on self-harm severity;* and the *Self-Harm Imagery Interview* (see Section 3.7). All measures will be collected using Qualtrics, either on the researcher's laptop if in person, or by sending the participant links to the questionnaires via the Imperial Zoom chat.

At the end of the Baseline Screening Visit, the researcher will ask the participant if they have any further questions about the study or therapy sessions, and check that the participant feels ok before ending the visit. If the participant is upset for any reason, the researcher will follow risk assessment procedures outlined in section 4.1 Risks and Benefits, and contact the duty clinician when necessary. The researcher will inform the participant that the therapist will contact them within 2 weeks to book in the first therapy session.

Finally, the researcher shares the baseline RCADS/DASS-21 measure with the therapist, CWP or CAPT, who then administer the RCADS (most salient subscale/s) or DASS-21, as applicable, at each therapy session to track symptoms.

Informing Clinicians of Young Person's Participation

A standard email informing of their taking part in the study is sent by the research team to the lead clinician involved in their routine care named by the participant, and the participant's referrer into the study (if applicable and different from the above).

Intervention Phase

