measurement of suicidal ideation and behaviour. The *Lifetime/Recent* version will be used at screening to gather recent history of suicidality including suicidal ideation and/or behaviour. The scale measures four constructs: severity of ideation on a 5-point ordinal scale (from 1=wish to be dead, to 5=suicidal intent with plan); intensity of ideation via 5 items (e.g. frequency, duration etc.), each rated on a 5-point ordinal scale; behavior rated on a nominal scale (including actual, aborted, and interrupted attempts, preparatory behavior and non-suicidal self-injurious behavior); and lethality rated on a 6-point ordinal scale. **This measure will additionally be used at the start of each face-to-face FIT session.**

e) Motivation to reduce self-harm: Using the State Motivation for Reducing Self-harm (SM-SH) scale (Parham et al., 2017). This scale measures participants' motivation to control their self-harm using 12 items that measure the strength of their motivational cognitions in the present moment, rated on a 10-point likert scale, from 0 (never) to 10 (constantly).

Self-report:

f) Urge to self-harm: Using the Craving Experience Questionnaire for Self-Harm (CEQ-SH), adapted from CEQ (May et al., 2014) This questionnaire assesses the urge to self-harm and assesses frequency, intensity, salience or dismissability of intrusive thoughts surrounding self-harm. It is rated on a 10 point Likert type scale ranging from not at all (0) to constantly (10).

Clinical and functional measures

Self-report:

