- a) Symptoms of low mood and anxiety: using 1) the Revised Children's Anxiety and Depression Scale (RCADS) for 12 17 year olds, is a 47 item youth self report questionnaire with six subscales (separation anxiety disorder, social phobia, generalised anxiety disorder, panic disorder, obsessive compulsive disorder, and low mood (major depressive disorder)) and a total anxiety scale and total internalising scale. The RCADS has good internal consistency, test-retrest reliability and convergent validity. 2) the Depression, Anxiety and Stress Scale (DASS-21) (Antony et al., 1998), for 18 25 year olds, a 21-item scale measuring levels of depression, anxiety and stress over the past week. It has acceptable to excellent internal consistency validated in both clinical and non-clinical samples. The depression scale measures symptoms associated with dysphoric mood e.g. worthlessness; the anxiety scale measures symptoms associated with physiological arousal such as trembling, as opposed to symptoms of generalised anxiety; and the stress scale measures symptoms of tension and reactivity to stressful events;
- b) **Psychological wellbeing:** using the Warwick-Edinburgh Mental Well-being Scale (WEMWBS) (Tennant et al., 2007), which consists of 14 positively worded items. Items are rated on a 5 point likert scale ranging between none of the time (1) and all of the time (5) with five

response categories and assesses mental wellbeing covering both hedonic and eudemonic perspectives.

- c) **Emotion regulation abilities:** using the *Difficulties in Emotion Regulation Scale-Short Form* (Kaufman et al., 2016), an 18-item scale adapted from the original long version that measures general emotion regulation ability as well as various aspects of emotion regulation (in six subscales), e.g. difficulties engaging in goal directed behaviour when upset, and limited access to emotion regulation strategies. The scale has high internal consistency.
- d) **Engagement in other risky, self-destructive behaviours** (e.g., binge eating, substance misuse): using the *11-item behaviour supplement to the Borderline Symptom List* (Bohus et al., 2001). The scale has high internal validity and test-retest reliability.

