2.9 DATA ANALYSIS

Sample Size

We aim to reach N=15 participants who will complete treatment and 6 months follow-up assessments. Based on an expected 25% attrition rate from our previous study ([name] et al., 2020), N=20 participants will be enrolled in the study.

Statistical Analysis

Quantitative data will be summarised into descriptive statistics such as means, medians, inter quartile range, standard deviations for all measures and percentage change and Cohen's *d* for the clinical outcomes repeated at pre- and post-intervention. Qualitative data will be analysed using a co-produced thematic analysis approach based on Braun & Clarke (2006) and Dewa et al. (2021a, 2021b). Data and all appropriate documentation will be stored for a minimum of 10 years after the completion of the study, including the follow-up period.

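### The pre-FIT value is taken at screening with no stated limit on the wait to session 1, so change during the wait is included in the reported pre-post change; session scores that could show it enter no change endpoint

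*Combined protocol and SAP*

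**What the plan says.** Section 2.4 defines the effectiveness and mechanism endpoints as "Change assessed from pre-FIT intervention to post-FIT intervention, and at 6 months follow up". It does not date the pre-FIT value. Section 2.8 lists the repeated measures as taken at the Baseline Screening Visit and then at the two outcome assessments, so screening supplies the only pre value.

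Section 2.7 has the researcher tell the participant at the end of screening that "the therapist will contact them within 2 weeks to book in the first therapy session". No maximum interval to session 1 and no repeat baseline are given. The same section times the 6-month visit from the start of the intervention, not from screening.

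Two kinds of score are collected during treatment. Under section 2.7 the treating clinician is to "administer the RCADS (most salient subscale/s) or DASS-21, as applicable, at each therapy session to track symptoms". Under section 2.8 the C-SSRS will "additionally be used at the start of each face-to-face FIT session", and section 2.7 gives its purpose there as assessing risk and adverse events. The DASS-21 is described as "a 21-item scale measuring levels of depression, anxiety and stress over the past week".

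Section 2.9 plans descriptive summaries, with percentage change and Cohen's d for clinical outcomes measured before and after the intervention. There is no comparator and no hypothesis test. Neither section 2.4 nor section 2.9 gives the session scores a role in measuring change, and the list of study data in section 3.5 does not name them.

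**The concern.** A participant's level can move between screening and session 1, before any FIT is given. With screening as the only baseline, that movement is reported as pre- to post-FIT change.

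Some movement is plausible. Entry under section 2.6 selects on recent or frequent self-harm, and standard care continues. Section 2.7 also lets participants offered another low-intensity intervention choose whether to take IMAGINATOR before or after it, and does not say that screening must follow that intervention. The DASS-21 looks back one week, so a score two or more weeks old does not describe the week before FIT began.

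Because follow-up is anchored to the start of the intervention and baseline to screening, the interval over which change is measured also differs between participants by a gap that the plan does not ask to be reported. In a single-arm series, a session-1 score is the only within-person value that could separate the wait from the treatment period.

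**Working it through.** **1. The plan's own figure.** Section 2.9 states "We aim to reach N=15 participants who will complete treatment and 6 months follow-up assessments", then "Based on an expected 25% attrition rate from our previous study", and concludes "N=20 participants will be enrolled in the study". 15 / (1 − 0.25) = 20, which agrees. No alpha, power or standard deviation is stated, so there is nothing further to reproduce, and this point leaves N unchanged.

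**2. Weeks from session 1 to the post assessment (s).** FIT sessions are weekly, in weeks 1, 2 and 3. There are five calls, the last four at fortnightly intervals, and the post assessment is the week after the last call. The documents date the first call in two ways, which must be reconciled:
- Section 2.5, week 4: calls in weeks 4, 6, 8, 10, 12; post in week 13; s = 13 − 1 = 12.
- Section 2.7, one week after the second FIT session (week 3): calls in weeks 3, 5, 7, 9, 11; post in week 12; s = 12 − 1 = 11.

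**3. Share of the screening-to-post interval spent waiting.** Share = g / (g + s), where g is the gap in weeks from screening to session 1. The documents do not give g; the values below are assumptions.

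| g (weeks) | s = 12 | s = 11 |
|---|---|---|
| 0 | 0% | 0% |
| 2 | 2/14 = 14% | 2/13 = 15% |
| 4 | 4/16 = 25% | 4/15 = 27% |
| 8 | 8/20 = 40% | 8/19 = 42% |

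**4. Scale in effect-size units (worst case).** Section 1 reports d = 0.65-0.75 from the proof-of-concept study, used here only as a reference scale. If a d of that size were entirely steady drift, the wait would supply d × share:
- g = 2: 0.65 × 2/14 = 0.09 to 0.75 × 2/13 = 0.12
- g = 4: 0.65 × 4/16 = 0.16 to 0.75 × 4/15 = 0.20
- g = 8: 0.65 × 8/20 = 0.26 to 0.75 × 8/19 = 0.32

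**5. Could pre and post values alone reveal this?** Taking d as a paired d (section 2.9 does not say which form), the exact noncentral-t 95% interval at n = 15 is 0.08 to 1.20 for d = 0.65 and 0.16 to 1.32 for d = 0.75. A waiting-period shift of 0.1 to 0.3 cannot be distinguished within intervals that wide.

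**6. Self-harm frequency.** This uses a 3-month recall, about 13 weeks. The post window reaches back 13 − 12 = 1 or 13 − 11 = 2 weeks before session 1. With a 4-week gap, 3 or 2 waiting weeks fall in neither window; with 8 weeks, 7 or 6 do. Episodes in those weeks are not themselves counted as change; only a shift in underlying level carries through.

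**7. What the session scores cover.** They cover the DASS-21, the salient RCADS subscale(s) and the C-SSRS. Self-harm frequency and severity, urge, imagery, emotion regulation and wellbeing are not listed as taken at session 1.

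**The case against.** The strongest reply is that little turns on this. The study is a descriptive, uncontrolled case series, and the affected endpoints are secondary and labelled as potential effects. Feasibility and acceptability are untouched. Drift and standard care during the 11-12 weeks after session 1 are just as unseparated, so a session-1 anchor would not make the remaining change attributable to FIT. The total participation time of about six months in section 2.7 also loosely suggests a short gap. All of that stands, and it limits the weight of the point. It does not answer it, because six months is no bound on the wait and the gap is not reported.

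The session scores also have weaknesses. They are administered by the treating clinician, whereas study measures are collected by a researcher via Qualtrics. Section 2.7 places DASS-21 or RCADS at the session, not before its content. RCADS subscales are chosen as most salient; if that means the highest at baseline, regression to the mean would enlarge the apparent fall to session 1. These are reasons to show the session values beside the planned change and not in place of it.

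Three stronger readings are tempting, and the documents do not support them:
- A reader might infer that the session C-SSRS enters no endpoint. Section 2.7 uses it to assess adverse events, and those recorded at sessions form the primary safety endpoint in section 2.4. It is absent only from the change endpoints.
- A reader might infer that the 5 expected losses (20 − 15) would have no value after baseline. The 15 are those completing both treatment and the 6-month assessment, so some of the other 5 may have a post-intervention visit. Section 2.4 defines attrition at that earlier visit.
- A reader might infer that the reported change could be twice the change after FIT began. Under steady drift a 50% waiting share needs g = s, a wait of 11-12 weeks, and the documents give neither a gap nor a drift rate.

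**Conclusion.** The point holds in a limited form. The screening visit is the only pre value for the change endpoints, the two-week limit applies to booking and not to session 1, and scores already collected at the sessions enter no change endpoint. Change in level during the wait is therefore included in the reported pre-post change.

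Its size is unknown. Waiting would make up 14-15%, 25-27% or 40-42% of the screening-to-post interval for assumed gaps of 2, 4 or 8 weeks. These are shares of time; they become shares of the change only if drift is steady, which is a further assumption. The consequence is confined to the secondary, exploratory endpoints. The remedy is cheap enough to be worth making, though session scores can address only the DASS-21, the salient RCADS subscale(s) and the C-SSRS.

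**What to change.** In sections 2.4 and 2.9:
- Define the pre-FIT value, and report days from screening to session 1 for all participants.
- Keep the planned screening-to-post change. Beside it, report screening-to-session-1 change and change from session 1 to post and to 6 months, for the DASS-21, the same RCADS subscale(s) and the C-SSRS.
- List the last session value for any participant without a post-intervention visit.

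In sections 2.7, 2.8 and 3.5:
- Have DASS-21 or RCADS completed before session 1 content begins.
- Transfer the session scores to the study dataset and name them in the data list.
- Section 2.8 names the C-SSRS version only for screening. State the reference period at each occasion, so that like is compared with like.

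The cost is a data transfer, one timing instruction and a few table rows, with no new visit, instrument or participant. The report should state the downsides: the split covers only these three measures; session scores are clinician-administered; salient RCADS subscales may regress to the mean; drift after session 1 remains unseparated; and the stated improvement may become smaller.

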2.5 STUDY DESIGN

IMAGINATOR is a case series study describing FIT as a low intensity intervention alongside standard care (SC) in a sequential sample of YP referred to any WLT team, in addition to CCAMHS or MINT.

The design includes the following elements and study phases:

- 1. Baseline Screening Visit
- 2. Intervention: 3 x 1 hour FIT sessions delivered face-to-face by a Child Wellbeing Practitioner (CWP), Clinical Assistant Psychology Therapists (CAPT) or therapist
- 3. Follow up: 5 x support sessions delivered over the phone (the first one in week 4, then fortnightly)
- 4. Smartphone app-based reminders, exercises and support from the second FIT session
- 5. Outcome assessments within a week of final session (at the end of intervention), and at 3 months post intervention
- 6. User-led feedback interviews with participants upon study completion (after final assessment).

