2.6 PARTICIPANTS

Participants are young individuals aged 12 to 25 years old who experience current repeated selfharm behaviour and are seeking support to manage and reduce self-harming via local mental health services.

Inclusion Criteria

- 1. Aged 12 25 years old
- Presented with at least 2 episodes of self-harm lifetime, with at least 1 of these in the past month OR 5 episodes of self-harm in the past year (based on NSSI Disorder criteria in the DSM-5) and currently reporting self-harm urges or difficulties stopping
- 3. Have a smartphone
- 4. Can commit to attending 3 consecutive weekly FIT sessions, and 5 follow-up telephone sessions, and assessments over follow up period as required by the study
- 5. Have adequate English language ability to permit the assessment and experimental measures to be completed, and use the smartphone app
- 6. Willing to consent to receive support to reduce / improve management of self-harm urges and behaviour; in person or by video, and over the phone and via smartphone app
- 7. If 12 15 years old, willing for parent/guardian to provide consent to study participation
- 8. Willing to have letters sent/phone calls made to relevant clinicians
- 9. Resident within geographical areas covered by West London NHS Trust.

Exclusion Criteria

The participant may not enter the study if any of the following apply:

- 1. Severe learning disability or pervasive developmental disorder
- 2. Current acute psychotic episode
- 3. Current substance dependence

- 4. Imminent risk of suicide or harm to others (based on clinicians' risk assessment, see Section 4.1)
- 5. Insufficient English language fluency to complete study outcome measures
- 6. Taking part in concurrent treatment studies investigating pharmacological or psychological treatment for self-harm
- 7. Unwilling to engage actively in the FIT intervention or to use an imagery-focused approach for treatment
- 8. Unwilling to use a smartphone app.

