After reviewing their formulation of drivers for self-harm and motives to change, participants are encouraged to identify in detail advantages of reducing self-harm. For example, they are asked to recall and visualise memories of occasions when they didn't self-harm and associated positive aspects, and to imagine future short-term and long-term scenarios of successful goal achievement (e.g. "how I would be in a year's time if I stopped self-harming"). Mental imagery is used to simulate positive aspects of behavioural change and thus support motivation for change. At the end of the session participants are asked to commit to the change by completing a homework task that consists of taking a photo of something that represents their target or goal for change.

In this session, the young person will also identify other key goals they want to work towards in the therapy and record these using a 'goals measure'. Progress in working towards these goals will then be reviewed and measured in the following sessions.

The second FIT session focuses on developing a plan of an alternative behaviour to self-harm and on functional imagery training to support this goal. In this session the goal is made concrete and translated into a short-term plan, i.e. something to be done in the next few days / week as an alternative to self-harming (e.g. "what I will do tomorrow to achieve my goal of managing anxiety without self-harming). Obstacles to change are discussed together with planning strategies to overcome them. Once a plan is outlined, participants are guided to practice it from beginning to end using mental imagery and are trained to harness mental imagery characteristics (e.g. vividness, realness) so that the imagery simulation amplifies motivation and drive to put in place the desired behaviour (e.g. "when I feel anxious, going for a short walk").

At the end of the second FIT session, participants download the *IMAGINATOR* app on their smartphone and are instructed on the app use to support practicing the functional imagery developed in session (see below). Finally, the first support call is scheduled in one week time.

The third FIT session focuses on discussing how practicing the functional imagery went, and problem-solving ways to improve the imagery plan. The therapist will work with the young person to fine tune the imagery, to help enhance any beneficial effects the imagery may have on emotion regulation.

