To assess risk and adverse events, at the beginning of each session the therapist conducts the Columbia-Suicide Severity Rating Scale (C-SSRS) interview.

Follow-up Phase

Follow up and support sessions: The Follow Up phase involves five support phone calls by the therapist/CWP/CAPT who conducted the FIT. The first phone support takes place one week after the second FIT session (approx. 30 mins duration). This session focuses on refining the functional imagery practice and problem-solving obstacles to training the imagery techniques. Suggestions - aim to incorporate the *IMAGINATOR* app as much as possible if the participant feels this is useful, for example discussing how the different app functionalities can be used, personalised and maximised to support the FIT.

Four further phone support sessions (approx. 15 mins each) are then delivered fortnightly, which focus on further problem-solving, motivational encouragement and discussion of how to maximise the *IMAGINATOR* app use.

To assess risk and adverse events, the therapist will conduct a clinical risk assessment at the beginning of each phone session.

IMAGINATOR app-based support: The IMAGINATOR app was co-designed with YP with lived experience of self-harm (see 2.2. Co-production). It is used by participants as a support to keep practicing and training FIT to achieve their behavioural change goal during the study follow-up IMAGINATOR 2.0

phase. The IMAGINATOR app does not introduce any new element from what has been discussed and developed in the FIT face-to-face sessions and is neither intended to nor designed to be used as a self-standing tool. To ensure confidentiality, the IMAGINATOR app makes no reference to self-harm and all push-ups and notifications only refer to 'IMAGINATOR'.

Routine follow-up: The therapist/CWP/CAPT) will follow up routinely with the young person at 16 – 18 weeks.

Outcome Assessments (post intervention and 6 months follow-up)

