All participants complete outcome assessments post intervention (the week after the final telephone session) and at 6 months follow-up from intervention start (3 months after the end of the intervention). Outcome assessments are completed via video-call or in person depending on the participant's preference. Measures are collected using Qualtrics (see 3.7 Assessments and Questionnaires for measures). The participant completes the questionnaires on the researcher's laptop if in person, or by a link to the questionnaires sent through the Imperial Zoom chat.

The outcome measure of Emergency Department attendance following a self-harm episode will be collected via access to routine clinical records of West London NHS Trust where entries by Liaison Psychiatry clinicians are reported following Emergency Department assessments on the North West London Whole Systems Integrated Care Dashboard (as consented by participants). This would include communication of assessments conducted out of area.

Participant Feedback Interview (6 months follow-up)

Researchers and trained YPAG members will conduct semi-structured interviews face-to-face or via video-call. Given our small sample-size we will seek to interview 2/3 of participants consented into the study until data saturation is achieved. Interview topic areas will include experience of the intervention and of the research procedures and motivations/barriers in accessing and using the IMAGINATOR intervention. We will seek to include a diverse sample in terms of socio-demographic characteristics. A qualitative process evaluation focusing on app-usability and design will be conducted using an established co-production methodology (Dewa et al., 2021a, 2021b).

For the app component, interviews will explore:

- barriers and facilitators to use;
- use of imagery audios and of tracking symptoms/experiences;
- expectations about future use, design and functionality suggestions; and,
- ideas for implementation into different settings.

Supervision Arrangements

IMAGINATOR cases will be discussed as part of therapist/CWP/CAPTs' routine weekly individual case management supervision. In addition, the PI ([name]) will provide group clinical skills supervision focusing on the delivery of IMAGINATOR. All FIT sessions are audio recorded, which is routine practice in WLT for training purposes.

End of Study Definition

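### The first support call is dated in two conflicting ways; separately, on either date the 3-month self-harm count at the post visit can reach back before session 1, by about 7-14 days on the week-4 schedule if nothing is delayed

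*Combined protocol and SAP*

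**What the plan says.** **When the first call takes place.** Section 2.5 lists "5 x support sessions delivered over the phone (the first one in week 4, then fortnightly". Section 2.7 says, at the end of the account of session 2, that "the first support call is scheduled in one week time", and repeats under Follow-up Phase: "The first phone support takes place one week after the second FIT session". Section 2.1, the numbered list in Section 2.5 and the overview in Section 2.7 all place the phone support after the three face-to-face sessions.

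**Spacing.** Inclusion criterion 4 (Section 2.6) reads "Can commit to attending 3 consecutive weekly FIT sessions". After the first call, "Four further phone support sessions (approx. 15 mins each) are then delivered fortnightly".

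**Assessments.** Section 2.5: "Outcome assessments within a week of final session (at the end of intervention), and at 3 months post intervention". Section 2.7 (Outcome Assessments) places the first of these "post intervention (the week after the final telephone session" and the second "at 6 months follow-up from intervention start (3 months after the end of the intervention".

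**Look-back and analysis.** Sections 2.4 and 2.8 count self-harm frequency and rate its severity over the past 3 months at baseline, post-intervention and 6 months. Nothing ties the post look-back to session 1. Section 2.9 reports percentage change and Cohen's d from pre to post. Objective 1e (Section 2.3) asks whether the pre-to-post change is maintained at 6 months.

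**The concern.** There are two issues, and neither causes the other.

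1. *Delivery.* A therapist cannot hold the first call both in week 4 and one week after session 2. On the second reading a half-hour call falls when session 3 is due, and the two cover similar ground (how imagery practice is going and how to improve it).

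2. *Measurement.* If the post visit comes less than 3 months after session 1, a 3-month look-back includes days before treatment began. Episodes on those days count as post-intervention and pull the reported pre-to-post change towards zero. The 6-month look-back begins well after session 1, so the two follow-up values are not on the same footing. The comparison between them is tilted slightly towards apparent maintenance or further improvement.

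**Working it through.** **Inputs.** Sessions on days 0, 7 and 14, counted from session 1 (Section 2.6). Four further calls 14 days apart (Section 2.7). Post visit 0-7 days after the last call (Sections 2.5 and 2.7). Look-back of 3 months (Sections 2.4 and 2.8), taken as 91 days. Six months taken as 182 days. No delays.

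**The plan's own figure.** Equating 6 months from start with 3 months after the end implies an intervention of 182 - 91 = 91 days. The written intervals do not reproduce this: the last call falls on day 70, 77 or 84, depending on the reading (below).

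**Formulas.** Last call = first call + 4 × 14. Post visit = last call + 0 to 7. Pre-treatment days = 91 - post-visit day.

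| Reading of the first call | Last call | Post visit | Pre-treatment days | Share of 91 |
|---|---|---|---|---|
| Week 4 as day 21 (Section 2.5) | 77 | 77-84 | 7-14 | 7.7-15.4% |
| Week 4 as any of days 21-27 | 77-83 | 77-90 | 1-14 | 1.1-15.4% |
| Week 4 as day 28 | 84 | 84-91 | 0-7 | 0-7.7% |
| One week after session 2, day 14 (Section 2.7) | 70 | 70-77 | 14-21 | 15.4-23.1% |

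Taking 3 months as 90 or 92 days moves each count by 1 day. Each week of delay removes 7 days, reaching zero once the post visit is at day 91. Moving the Section 2.7 call to day 21 still leaves 7-14 days, so correcting the call date does not remove the overlap.

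**Effect on the reported change.** If pre-treatment days run at the baseline rate, reported drop = D × (1 - share), where D is the average drop since session 1. The documents give no D, so it is assumed:

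| Assumed D | 7-14 days (day 21) | 14-21 days (day 14) |
|---|---|---|
| 30% | 27.7-25.4% | 25.4-23.1% |
| 50% | 46.2-42.3% | 42.3-38.5% |
| 70% | 64.6-59.2% | 59.2-53.8% |

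With week 4 as day 28, a 50% drop reads as 46.2-50%.

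**Six months.** A visit at day 182 looks back to 182 - 91 = day 91. Dated instead as last call + 91 (day 161, 168 or 175), it looks back to day 70, 77 or 84. All are after session 1, so this value is not diluted. With a constant 50% drop, post reads about 42-46% (day 21) and 6 months reads 50%. With the post visit at day 77, a true slip from a 50% to a 42% drop would look like full maintenance.

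**Scale.** At an assumed paired d of 0.7 with unchanged SD, the shift is 0.7 × 0.077 = 0.05 to 0.7 × 0.154 = 0.11 on the day-21 schedule, and up to 0.7 × 0.231 = 0.16 on the day-14 schedule. With the 15 completers targeted in Section 2.9, the 95% half-width is 1.96 × √(1/15 + 0.49/30) = 0.56.

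**The case against.** The best defence is that the intervals are approximate and the look-back is deliberately equal at all three visits.

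- *Timing.* The overlap needs weekly sessions, punctual calls and a prompt post visit. On the day-21 schedule, one to two weeks of total slippage removes it. The documents give no data on actual timing, so the real overlap is unknown. This stands: the day counts describe the plan as written, not a forecast.
- *Equal windows.* The protocol never defines the post measure as the period since session 1, and equal recall length is a sound choice. This is why the 3-month count should be kept. Nor is session 1 the only possible boundary: the alternative-behaviour plan and the app begin at session 2. A boundary there, at day 7, would add 7 days to the overlap.
- *Baseline rate.* Rates may already be falling between baseline and session 1. The factor (1 - share) would then overstate the dilution. This also stands.
- *Importance.* The outcome is secondary and analysed descriptively, with no test or success threshold, and the shift in d is small beside its uncertainty. This limits the weight of the point but does not make the bias directionless.

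A reader might infer that 14-21 days is the expected overlap because two places in Section 2.7 agree on the earlier call. The documents do not support that. Those two statements put the call on top of session 3 and go against the order given in Sections 2.1, 2.5 and 2.7 (overview), so the week-4 schedule is the more credible. Nor does the call-date conflict produce the overlap: switching schedule moves it by only 7 days.

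**Conclusion.** Both points hold, at modest size.

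1. The first-call date in Section 2.7 conflicts with Section 2.5 and should be corrected.
2. As written, and without delays, the post-visit frequency count includes about 7-14 pre-treatment days (8-15%) on the week-4 schedule. It includes 0-7 if week 4 means day 28, and 14-21 only if Section 2.7 is followed literally.

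The reported pre-to-post drop shrinks in proportion, so an assumed 50% reads as about 42-46% at 7-14 days. The error is conservative for that change. It is not conservative for objective 1e, where a diluted post value is set against an undiluted 6-month value.

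These figures rest on a 91-day look-back, on-time delivery and pre-treatment days at the baseline rate. It would go too far to conclude that the pre-to-post result is invalid or that the study's main conclusions are at risk: the primary feasibility, acceptability and safety endpoints do not use this window. This is a cheap improvement to a secondary descriptive outcome.

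**What to change.** - *Call date.* In both places in Section 2.7, put the first call one week after the third FIT session (week 4, counted from session 1).
- *Dates.* Record the dates of session 1, each call and each assessment.
- *Frequency.* At the post visit, have researchers mark session 1 on the timeline follow-back calendar and split the count there. Report the since-session-1 frequency per 30 days beside the baseline rate per 30 days, in addition to the 3-month count. Add a sentence to Sections 2.4 and 2.9.
- *Severity.* Keep it on the 3-month window. Worst injury and number of methods depend on window length and cannot be rescaled, so a shorter window would lower them with no true change. State in the report that post severity still includes some pre-treatment days.

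**Cost.** A wording edit in two places, two added sentences, one extra derived variable and a short interview instruction. No extra visit is needed. Section 2.8 describes counting episodes with calendar cues but does not say that each is dated, so the split has to be asked for and may add a little interview time. The shorter window loses some precision: if episodes are Poisson (assumed), the standard error of the post rate widens by √(91/84) = 1.04 to √(91/70) = 1.14, or about 4-14%.
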